Cover page

Title of study: Assessment of Endogenous Oxalate Synthesis

IRB-151020005

NCT05229952

Document date: 12/08/24

STUDY PROTOCOL

Objective of the study

The objectives of this study were to determine endogenous oxalate synthesis rates by continuous intravenous infusion of ¹³C₂-oxalate (a stable isotope of oxalate) and to identify surrogate methods of estimating this parameter using urine collections on a low-oxalate normal calcium fixed diet.

[figure not shown]
Study Design

The study recruited adults from the Birmingham area for a low oxalate controlled diet. The individuals were recruited, consented, and had blood samples collected at the UAB CCTS Clinical Research Unit. Sample processing, data acquisition and analysis was performed in the Urology Stone Research Laboratory. A total of 20 participants was expected. An equal number of males and females was planned from all ethnic backgrounds. The study corresponded to a BESH trial (Basic Experimental Study in Humans). All enrolled participants received the same intervention defined as a period of fixed diet followed by the infusion of ¹³C₂-oxalate.

- Inclusion criteria: mentally competent adults, who are able to read and comprehend the consent form (written in English); >18 and <75 yrs; BMI 18.5-50 kg/m2; good health as judged from a medical history without other medical comorbidities. individuals will need a normal blood comprehensive metabolic panel. With of without history of calcium oxalate kidney stones
- Exclusion criteria: history of any hepatic, renal (including kidney stone disease), bowel or endocrine disease (including diabetes) or any other condition that may influence the absorption, transport or urine excretion of ions, which will compromise the interpretation of results; abnormal blood metabolic profiles; poor 24 hour urine collections judged by 24 hour urine creatinine excretion (indicative of not collecting all urine in 24 hour period); pregnancy, intention to become pregnant in the near future, or lactation; <18 and > 75 years of age; BMI<18.5

Study Methods

The study sequence is profiled in figure below.

Study sequence overview. After a screening period on self-choice diet, which included two 24-hr urine collections (♦) and a blood draw, participants ingested a fixed low-oxalate, normal calcium diet for a total of 5 days (shaded boxes). The ¹³C₂- oxalate infusion was performed in the fasted state, following 4 days of dietary equilibration and two 24-hr urine collections. Participants collected one pre-infusion hourly urine, and 6 hourly urines during the infusion, and a post infusion 6-hr and 12-hr collection, the aggregate comprising a 24-hr collection. Blood (↑) was collected before the infusion and every 30 minutes during the infusion. Consumption of the fixed low oxalate diet was resumed at the end of the 6-hr infusion and the study ended at the completion of the 24-hr urine collection on the morning of day 6.

 Screening. A fasted blood was drawn for comprehensive metabolic panel. Two 24-hour urine were collected on self-choice diets to assess participant's skill at completing 24-hourb urine collections. Body composition was measured by impedance (segmental body composition estimated by impedance, BC-

Version 12/08/2024 Study IRB151020005

418 segmental body composition analyzer, TANITA). A DEXA scan was performed at the end of the study to assess body composition more accurately.

- Fixed Diet and infusion Study:
- Participants ingested fixed, isocaloric diets (2000 or 2500 kcal/day) containing a low amount of oxalate (30 50 mg/day), normal calcium (1000 1120 mg/day), and normal ascorbic acid intake (90-125 mg/day) for 5 consecutive days. The low-oxalate diet was prepared in a metabolic kitchen at UAB. Participants were asked to refrain from vigorous exercise during the study. After 2 days of dietary equilibration, two 24-hr urine were collected, followed by a primed, steady-state infusion of ¹³C₂-oxalate.
- On Day 5, following a 10-hr overnight fast, and waking at 6:00 a.m., participants emptied their bladders and drank 500 ml of water. Participants were admitted to the Clinical Research Unit (CRU) at 7:00 a.m to start the oxalate infusion.
- Primed, ¹³C₂-oxalate, continuous, intravenous infusion. The intravenous infusions were initiated at 8:00 a.m. with a priming dose of sodium ¹³C₂-oxalate administered over a 10 min period in 0.9% saline (equivalent to a 1.5 to 2 hr dose). This was immediately followed by a constant infusion of ¹³C₂-oxalate for up to 6 hrs (0.022 μmol/kg/h) in the fasted state. Separate catheters on opposite arms were used for the infusion of ¹³C₂-oxalate and blood collections. Serial urine (hourly) and plasma (every 30 min) samples were be collected between 1 hour prior to and 6 hours after the start of the infusion. The remainder of the 24-hr urine that day was collected until the following morning. Urine output was maintained during the infusion by having participants drink 200 ml of bottled water per hour. Blood and urine samples were collected every half-hour and hour, respectively. At the end of the infusion (6 hrs), food consumption was resumed and the remainder of the 24-hr urine for that day was collected. Final concentrations of ¹³C₂- oxalate in 0.9% saline infusion bags were measured by ion chromatography coupled with mass spectrometry, and the recovery of intravenously infused ¹³C₂-oxalate in urine collections was calculated both during the steady-state period and the 24 hours following initiating infusion.
- Assays. ¹²C- and ¹³C- isotopomers of oxalate in urine, plasma and food extracts were measured by lon Chromatography coupled with Mass Spectrometry. Urine and plasma sample handling and storage follow strict protocols to avoid crystallization of oxalate or vitamin C breakdown to oxalate (leading to under or overestimation of oxalate). The analysis of 24-hr urine collections included: volume, urine oxalate measurement by lon Chromatography coupled with Mass Spectrometry, and creatinine.

STATISTICAL ANALYSIS PLAN

The primary outcome measure was endogenous oxalate synthesis as measured by the $^{13}C_2$ -oxalate continuous infusion, measured in mg/day.

The formula for the calculation endogenous oxalate synthesis oxalate is

Oxalate Synthesis Rate $(mg/day) = \{i \times [(Ei / EOx) - 1]\} \times 90.02 \times 24 \text{ hours}/1000$

where "i" is the tracer infusion rate in µmol/hr; (Ei /EOx) is the ratio of the ¹³C₂-oxalate mole percent isotopic enrichment of the ¹³C₂-oxalate infusion solution (Ei: 99.6%) and the mole percent enrichment of plasma oxalate (EOx); and 90.02 g/mol represents the molecular mass of oxalate.

The secondary outcome measures were the mean 24-hr urinary oxalate excretions on the low-oxalate fixed diet measured in mg/day and in mg oxalate/g creatinine.

Exploratory endpoints were the association between endogenous oxalate synthesis rate, 24-hr urinary oxalate excretion on the fixed diet, body composition and hourly fasting urinary oxalate excretion.

Equilibration of plasma 13 C₂-oxalate over time was analyzed by repeated-measures one-way ANOVA. Comparison of endogenous oxalate synthesis between groups (BMI <30 vs \geq 30 kg/m², male vs female) was done with t-test. The linear relationships of endogenous oxalate synthesis with urinary creatinine and lean mass was assessed separately by ordinary least squares regression. Pearson correlation coefficients were calculated between endogenous oxalate synthesis, urinary creatinine, lean mass and gender. SAS software Version 9.4 was used in these analyses. The criterion for statistical significance was p<0.05 and all tests two-sided.

The sample sizes were selected based on feasibility considerations for this pilot Basic Experimental Study in Humans (BESH).

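### The primary-outcome formula uses 90.02 g/mol as the mass of oxalate, but oxalate is 88.02 g/mol, so rates computed as written are 2.3% too high

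*Combined protocol and SAP*

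**What the plan says.** The Statistical Analysis Plan section defines the primary outcome as endogenous oxalate synthesis in mg/day, obtained from the tracer infusion. In compact notation the formula is

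R = i × (Ei/EOx − 1) × 90.02 × 24/1000,

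where i is the tracer infusion rate in µmol/hr, Ei is the enrichment of the infusate (99.6 mole percent) and EOx is the enrichment of plasma oxalate. The constant is explained by the statement that "90.02 g/mol represents the molecular mass of oxalate". The value 90.02 appears both in the formula and in this explanation, so a misread character is unlikely.

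The secondary outcomes are the "mean 24-hr urinary oxalate excretions on the low-oxalate fixed diet measured in mg/day and in mg oxalate/g creatinine". No molecular mass is given for them. The exploratory endpoints relate synthesis to urinary oxalate excretion, among other variables. The planned tests are t-tests, ordinary least squares regressions and Pearson correlations.

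**The concern.** The value and its label do not match: 90.02 is not the molecular mass of oxalate. The constant multiplies the primary outcome of every participant, so an error in it is a systematic bias that a larger sample would not reduce.

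The absolute value matters here because the study's first objective is to determine synthesis rates. The second is to find urine-based surrogates for that rate, which calls for synthesis and urinary excretion on the same mass scale. If urinary oxalate is converted with 88.02 and synthesis with 90.02, excretion would appear to fall short of synthesis by about 2.2% for no biological reason.

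**Working it through.** **Inputs.** From the plan: the formula, the constant 90.02, Ei = 99.6%, and the infusion rate of 0.022 µmol/kg/h (Study Methods, infusion paragraph). From general chemistry, not the documents: atomic masses C 12.011, O 15.999, H 1.008, ¹³C 13.00335.

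**Step 1: try to reproduce 90.02.**

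| Species | Calculation | g/mol |
|---|---|---|
| Oxalate, C₂O₄ | 2 × 12.011 + 4 × 15.999 | 88.018 |
| Hydrogen oxalate, HC₂O₄ | 88.018 + 1.008 | 89.026 |
| Oxalic acid, H₂C₂O₄ | 88.018 + 2 × 1.008 | 90.034 |
| ¹³C₂-oxalate, exact ¹³C mass | 2 × 13.00335 + 4 × 15.999 | 90.003 |
| ¹³C₂-oxalate, nominal | 88.018 + 2 | 90.018 |

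The stated figure does not reproduce for oxalate. It does reproduce, after rounding, for the labelled tracer with a nominal shift of 2, and it lies within 0.02% of oxalic acid.

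**Step 2: which species does the formula convert?** Total appearance of oxalate is i × Ei/EOx. Subtracting i, which is what the −1 does, removes the infused tracer. What remains is endogenous oxalate with ordinary carbon, so the tracer's mass does not apply and 88.018 does.

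**Step 3: check the rest of the formula.** µmol/hr × g/mol gives µg/hr; × 24 gives µg/day; ÷ 1000 gives mg/day. The dilution term and the unit conversion are sound. Only the mass is at fault.

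**Step 4: size.** The mass is a single multiplier, so the ratio of printed to corrected rate is

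90.02/88.018 = 1.0227, or +2.27%.

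In reverse, the correction multiplies each rate by 88.018/90.02 = 0.9778, or −2.22%.

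**Step 5: worked example (assumed weight 70 kg, assumed EOx 20%).**

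- i = 0.022 × 70 = 1.54 µmol/hr
- Ei/EOx − 1 = 99.6/20 − 1 = 3.98
- 1.54 × 3.98 = 6.1292 µmol/hr
- With 90.02: 6.1292 × 90.02 × 24/1000 = 13.24 mg/day
- With 88.018: 6.1292 × 88.018 × 24/1000 = 12.95 mg/day

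Over weights of 60, 70, 80 and 100 kg and EOx of 15, 20, 25 and 30% (all assumed), the ratio is 1.02275 in all 16 combinations.

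**Step 6: effect on the planned analyses.** A constant factor cancels from t statistics, Pearson coefficients and regression p-values. In simulated data for 20 people, rescaling left the t-test p-value (0.162), the correlation (−0.338) and the regression p-value (0.145) unchanged, while the slope moved from −0.0826 to −0.0808. Means, SDs, confidence limits, group differences in mg/day, and slopes and intercepts with synthesis as the outcome all scale by the same factor.

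**The case against.** The strongest objection is that the constant may be right and only the word wrong. At 90.02 against 90.034, the values would be correct to about 0.02% if the laboratory reports oxalic acid equivalents, which is a defensible convention. The documents do not rule this out, but they never state it: they speak of oxalate throughout, including in the unit "measured in mg/day and in mg oxalate/g creatinine". Even on this reading the plan needs correcting, in the label rather than the number.

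Second, the gap between synthesis and urinary excretion is conditional. No mass is given for the urinary conversion, and if the same constant was used for both there is no gap. The plan also lists only associations between the two, with no ratio, difference or agreement analysis, and associations are unaffected by scale. This stands. The urinary argument is a reason to state one common mass, not proof of a distorted result.

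Third, the effect is small for this study. With 20 participants the 95% half-width for a mean is 2.093 × CV/√20 = 0.468 × CV, which is ±7.0%, ±11.7% and ±16.4% for assumed between-person CVs of 15%, 25% and 35%. The CV would have to be about 5% for 2.3% to equal the half-width. This also stands and limits the practical weight, although sampling error does not excuse a known bias.

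Last, the document does not show which constant the computation used. The 2.3% therefore applies to the formula as printed; if the computation used 88.02, only the text is wrong.

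**Conclusion.** The concern holds. The constant in the primary-outcome formula is not the molecular mass of oxalate, and rates computed as written and read as mg of oxalate are overstated by 2.3%, equally for everyone. This rests on two assumptions: that mg/day means mg of oxalate, as the text says, and that the printed formula was the one used. No test result or correlation in the plan changes. The absolute synthesis rate, which is the study's first objective, does change. The error is small, but it sits in the definition of the primary outcome and should be corrected.

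**What to change.** Replace 90.02 with 88.02 g/mol in both the formula and its definition. State that the same mass converts urinary oxalate to mg/day and to mg/g creatinine. Then check which constant the analysis used. If it was 90.02, multiply the reported synthesis rates, means, SDs, confidence limits, group differences, and slopes and intercepts with synthesis as the outcome by 0.9778; if it was 88.02, only the text needs correcting.

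If oxalic acid equivalents were intended, say so, label the primary and urinary outcomes that way, and use 90.03 for both.

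The cost is one constant and a rescaling. No new data or assays are needed, and no p-value has to be recomputed.

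### The only stated equilibration analysis, a repeated-measures ANOVA with no window, drift limit or decision rule, is a poor check of the plateau that the primary formula needs

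*Combined protocol and SAP*

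**What the plan says.** The formula in the Statistical Analysis Plan multiplies the tracer infusion rate by (Ei/EOx - 1). Here Ei is the enrichment of the infusate and the denominator is "the mole percent enrichment of plasma oxalate (EOx". The plan does not say which plasma samples supply EOx.

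The Study Methods describe the fixed-diet collections as "followed by a primed, steady-state infusion of" labelled oxalate. They also say that urinary recovery of the tracer "was calculated both during the steady-state period and the 24 hours following initiating infusion". The start and end of that steady-state period are not defined.

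The prime is "equivalent to a 1.5 to 2 hr dose", and the constant infusion then runs for at most 6 h. Blood "was collected before the infusion and every 30 minutes during the infusion".

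On equilibration the Statistical Analysis Plan has one sentence: plasma labelled oxalate "over time was analyzed by repeated-measures one-way ANOVA". The general rule follows: "The criterion for statistical significance was p<0.05 and all tests two-sided". No window, contrast, slope, confidence interval, drift limit or reading rule is attached. The sentence also leaves open whether the variable is tracer concentration or mole percent enrichment; the formula uses the latter.

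**The concern.** The formula returns a participant's synthesis rate only when plasma enrichment is at plateau. The plan does not state this condition; it follows from the formula and from the steady-state wording. The null hypothesis of the ANOVA is that mean enrichment is equal at all times, which is a different question.

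- Over all infusion samples, rejection says that something changed at some time. It does not say whether the change had ended by the time EOx was taken.
- Over a late window, failure to reject is absence of evidence, and it becomes more likely as the assay gets noisier.
- In both uses the test concerns group means, whereas EOx enters the formula person by person.

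At stake are the primary outcome itself and every analysis built on it: the BMI and sex comparisons, and the regressions and correlations with creatinine and lean mass. An EOx below plateau overstates synthesis by more than its own error.

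**Working it through.** The plan gives no power, precision or plateau figure, so there is nothing to reproduce.

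**Inputs.** From the documents: 20 participants expected, half-hourly plasma samples, infusion up to 6 h, prime P of 1.5 to 2 h of infusion, 0.022 µmol/kg/h, two-sided 0.05. Assumed, because the documents give none: CV 5%, 10%, 20% (all triplets below are in this order); turnover time τ of 1 to 3 h; 70 kg; true synthesis 15 mg/day. Errors are independent on the log scale with variance σ² = ln(1+CV²) = 0.0025, 0.00995, 0.0392, and the ANOVA is uncorrected for sphericity.

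**1. Error passed through the formula.** Let k be synthesis divided by infusion rate. Infusion is 0.022 × 70 = 1.54 µmol/h; synthesis is 15/90.02 × 1000/24 = 6.94 µmol/h; so k is about 4.5. If EOx is a fraction m of plateau, bias = [((k+1)/m - 1)/k] - 1. With m = 0.90 this is +14.8%, +13.6% and +13.0% for k = 3, 4.5 and 6.

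**2. Late window, shared 5% rise over 3-6 h (7 samples).** The log slope is ln(1.05)/3 = 0.01626 per h, and Sxx = 7.0 h². The ANOVA noncentrality is λ = 20 × 0.01626² × 7.0/σ² = 14.8, 3.7, 0.94 on 6 and 114 df, giving power 0.81, 0.24, 0.09. A t-test on the mean of the per-person slopes has noncentrality √λ on 19 df and power 0.95, 0.45, 0.15. The signal is the same; the ANOVA spreads it over six degrees of freedom.

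**3. Bias in a one-pool model.** With the prime treated as instantaneous, tracer amount relative to plateau is f(t) = 1 + (P/τ - 1)e^(-t/τ), and EOx/plateau = (k+1)f/(f+k). The value m is its mean over the samples from 3 to 6 h.

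| τ (h) | P (h) | m | Bias in synthesis | Mean slope (%/h) |
|---|---|---|---|---|
| 1.5 | 1.5 | 1 | 0 | 0 |
| 1.5 | 2 | 1.017 | -2.0% | -1.0 |
| 2 | 1.5 | 0.976 | +3.1% | +1.2 |
| 2 | 2 | 1 | 0 | 0 |
| 3 | 2 | 0.935 | +8.5% | +2.3 |
| 3 | 1.5 | 0.901 | +13.4% | +3.7 |

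For the last row, ((5.5/0.901 - 1)/4.5) - 1 = 0.134. Varying k from 3 to 6 moves these biases by under 0.1 point.

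**4. ANOVA over all samples from 0.5 to 6 h.** With τ = 1 h and P = 1.5 h the 3-6 h bias is only -0.9%, yet the test is significant in 100%, 100%, 93% of studies. With τ = 3 h and P = 1.5 h (bias +13.4%) it is significant in 100% throughout. With prime matched to turnover it is significant in 5%, as it should be.

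**5. Late-window ANOVA on the largest bias (τ = 3 h, P = 1.5 h, 3-6 h).** It detects the drift in 100%, 92%, 31%; the slope test in 100%, 98%, 55%.

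**6. What a slope interval can deliver.** The 90% half-width is t(0.95, 19) × σ/√(20 × 7.0) = 0.7, 1.5, 2.9 %/h. A truly flat plateau has its interval inside ±2 %/h in 99.7%, 48%, 0.2% of studies, and inside ±3 %/h in about 100%, 92%, 12%. With τ = 3 h and P = 2 h (bias +8.5%), the interval still lies inside ±3 %/h in about 47% of studies at CV 5%.

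**7. A few drifting participants.** If 3 of 20 rise 20% over 3-6 h, the ANOVA flags it in 17%, 8%, 6% and the mean-slope test in 17%, 11%, 7%. Power to detect such a rise in one person is 73%, 26%, 10%.

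**The case against.** The best defence is that the design probably makes the problem small. In the one-pool model a prime of P hours puts tracer at plateau at once when turnover equals P, so a 1.5 to 2 h prime suggests that turnover was expected in that range. Bias is then -2.0% to +3.1%. The larger figures all need a turnover of about 3 h, which nothing in the documents indicates. This stands, although the expected turnover is itself an inference.

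A reader might infer that the ANOVA can never reveal a missing plateau, or that it always flags settled and unsettled infusions alike. Neither is supported. On a late window with CV 5-10% it would detect the largest bias shown, and with a matched prime the all-sample test keeps its 5% error rate.

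Nor does a slope interval prove a plateau by itself. It needs a stated bound, it is weak at CV 20%, and as a group mean it misses a few drifting participants about as often as the ANOVA does.

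Finally, this is a pilot study sized on feasibility. That justifies the sample size. It does not supply the missing window or reading rule for the condition on which the primary outcome rests.

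**Conclusion.** The concern holds in a limited form. The stated ANOVA is a poor check of plateau: without a window, drift limit or decision rule, a significant all-sample result and a non-significant late result both leave the question open, and a late slope with its interval answers it more directly. For a shared linear rise the slope test is also more powerful at every CV examined.

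The size of any harm is not established. Every CV, drift and turnover above is an assumption, and the one-pool model is a simplification. The documents do not support a reading that plateau was missed or that the reported synthesis rates are inflated by 10% or more. They support only that the stated analysis gives a reader little basis for ruling this out, particularly if the assay CV is high. The change is worth making because it is cheap and concerns the validity condition of the primary outcome.

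**What to change.** 1. State that EOx is the mean mole percent enrichment over a fixed window counted back from the end of infusion, since the infusion may run for less than 6 h; for example the last 3 h, 7 samples. Say that the equilibration analysis uses mole percent enrichment in that same window.
2. In place of or beside the ANOVA, report the mean slope of log mole percent enrichment over the window with its 90% confidence interval.
3. Judge it against a drift bound derived from the bias in mg/day that can be tolerated, and state the turnover assumed in the conversion: in the table above, 1.2 %/h goes with 3.1% bias at a 2 h turnover and 2.3 %/h with 8.5% at 3 h. A loose bound such as ±3 %/h can pass a slow rise with about 8% bias. An interval not contained in the bound means that a plateau was not shown; it does not mean that there was none.
4. List each participant's slope and interval descriptively. Any exclusion of drifting participants belongs in a sensitivity analysis only, labelled post hoc if the data have been seen.

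The cost is SAP wording and a short re-analysis of samples already taken. The downsides are fewer samples behind each EOx and an imprecise slope at high CV. Shortening the window to 2 h lowers the bias from slow turnover but widens the 90% half-width to 1.2, 2.4 and 4.8 %/h at CV 5%, 10% and 20% (Sxx = 2.5).

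### No listed analysis includes urinary oxalate, and no estimation error is planned for any surrogate, although one objective is to estimate oxalate synthesis from urine

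*Combined protocol and SAP*

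**What the plan says.** The protocol's section on the study objective gives two aims. The first is to measure the synthesis rate by tracer infusion. The second is to "identify surrogate methods of estimating this parameter using urine collections on a low-oxalate normal calcium fixed diet".

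The Statistical Analysis Plan carries urinary oxalate forward twice. The secondary outcomes are the "mean 24-hr urinary oxalate excretions on the low-oxalate fixed diet measured in mg/day and in mg oxalate/g creatinine". The exploratory endpoints are associations between the synthesis rate, "24-hr urinary oxalate excretion on the fixed diet, body composition and hourly fasting urinary oxalate excretion".

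The methods paragraph that follows lists four kinds of analysis:
- repeated-measures ANOVA of plasma tracer over time;
- t-tests of synthesis by BMI group and by sex;
- regression: "The linear relationships of endogenous oxalate synthesis with urinary creatinine and lean mass was assessed separately by ordinary least squares regression";
- correlation: "Pearson correlation coefficients were calculated between endogenous oxalate synthesis, urinary creatinine, lean mass and gender".

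On testing, it adds: "The criterion for statistical significance was p<0.05 and all tests two-sided". The sample size is 20, set by feasibility.

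**The concern.** The variables in the exploratory endpoints do not match those in the methods. Urinary oxalate is the obvious urine candidate for estimating oxalate synthesis. It does not appear in any listed analysis, whether in mg/day, per gram of creatinine or hourly.

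There is a second gap. To estimate a person's synthesis rate from urine, a user needs to know how far the estimate may be from the truth. The plan mentions no residual SD, prediction interval or other measure of estimation error, either for the unlisted urinary oxalate analyses or for the listed creatinine and lean mass models. A correlation and its p-value do not supply this. A correlation also cannot show a constant offset between two measures in the same unit, as synthesis and 24-hr oxalate are (mg/day).

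At stake is whether the report can say how well any urine measure estimates synthesis.

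**Working it through.** **Endpoints against methods.**

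| Quantity | Named as outcome or endpoint | In listed OLS | In listed Pearson |
|---|---|---|---|
| 24-hr urinary oxalate, mg/day | yes | no | no |
| 24-hr urinary oxalate, mg/g creatinine | yes (secondary) | no | no |
| Hourly fasting urinary oxalate | yes (exploratory) | no | no |
| Body composition (lean mass) | yes (exploratory) | yes | yes |
| Urinary creatinine | only as a denominator | yes | yes |

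The ANOVA concerns plasma tracer and the t-tests concern synthesis by group, so neither fills the gap.

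**Would adding urinary oxalate to the listed tests be enough?** The plan has no figure of its own to reproduce, since n = 20 rests on feasibility. Inputs: n = 20 (Study Design); two-sided p<0.05 (SAP). The documents give neither a correlation nor the SD of synthesis, so widths are in SDs of synthesis and r is taken over an assumed range.

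1. Smallest significant correlation: |r| = t/√(t² + 18), with t(0.975, 18) = 2.101. This gives 2.101/√(4.414 + 18) = 0.444.
2. 95% prediction half-width with no predictor: t(0.975, 19) × √(1 + 1/20) = 2.093 × 1.0247 = 2.14 SD.
3. 95% prediction half-width with one predictor, at its mean: t(0.975, 18) × √(1 − r²) × √(19/18) × √(1 + 1/20) = 2.212 × √(1 − r²) SD. This is the narrowest point; the interval widens away from the mean.

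| r | Half-width (SD) | Narrower than no predictor |
|---|---|---|
| 0.444 (just significant) | 1.98 | 7.6% |
| 0.6 (assumed) | 1.77 | 17.5% |
| 0.8 (assumed) | 1.33 | 38% |
| 0.9 (assumed) | 0.96 | 55% |

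4. To halve the interval, √(1 − r²) = (2.145/2)/2.212 = 0.485, so r = √(1 − 0.235) = 0.875.
5. Precision of the missing quantity: with 18 degrees of freedom, a residual SD has a 95% CI from √(18/χ²(0.975)) to √(18/χ²(0.025)), which is 0.76 to 1.48 times its estimate. This is wide, but it can be reported.

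**Which hourly urine?** The study sequence overview says: "Participants collected one pre-infusion hourly urine, and 6 hourly urines during the infusion". The infusion itself ran in the fasted state, so the hourly fasting endpoint could mean either set. The infusion urines also carry infused tracer. Taking the protocol's rate of 0.022 μmol/kg/h, assumed body weights of 60 to 100 kg and full excretion, the constant infusion alone adds 0.022 × 60 × 24 × 90.02/1000 = 2.9 to 0.022 × 100 × 24 × 90.02/1000 = 4.8 mg/day equivalents. Total oxalate in those urines would therefore overstate the unlabelled amount.

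**The case against.** The strongest reply is that this is an incomplete variable list. The exploratory endpoints are worded as associations, Pearson and OLS are the association methods given in the same section, and applying them to urinary oxalate is the natural reading. That is fair, and a reader should not infer that the plan forgot urinary oxalate. But no listed method names it, and the natural extension would still report no estimation error.

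It can also be said that urinary creatinine is a urine measure and is already regressed, and that OLS yields an estimating equation from which residual SD and prediction intervals follow. Both points stand. The objective is partly addressed and OLS is a suitable tool; what is missing is a commitment to report those quantities and to use them.

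A reader might infer that the plan will accept any surrogate that reaches p<0.05. The documents do not say so. They state a general significance criterion and no rule for accepting a surrogate. The figures above show what a significant r does and does not convey; they do not describe a decision rule in the plan.

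The study is also a feasibility-sized pilot that aims to identify surrogates, not validate them. This limits the severity. It does not remove the point, because in a small sample a bare significant correlation looks more informative than it is.

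Finally, one might demand limits of agreement. That goes too far. The diet is described thus: "Participants ingested fixed, isocaloric diets (2000 or 2500 kcal/day) containing a low amount of oxalate". Participants ate it while the 24-hr collections were made, whereas synthesis was measured fasting. A difference between the two can therefore include absorbed dietary oxalate and is not surrogate error alone. A surrogate calibrated by regression also need not equal synthesis in mg/day.

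**Conclusion.** The concern holds in a limited form. No listed analysis includes urinary oxalate, although the objective and the endpoints call for it, and no estimation error is planned for any candidate surrogate. Extending the listed tests would leave the second gap open: at n = 20 a just-significant correlation narrows the 95% prediction interval by about 8%, and halving it takes r of about 0.875.

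The prediction figures assume 20 evaluable participants, a linear relation with normal errors, and prediction at the mean of the predictor. The values of r are illustrative, so the figures do not predict how any candidate will perform here.

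The documents do not support the stronger conclusions that the surrogate objective is left wholly unaddressed, that OLS and Pearson are wrong for an association endpoint, or that the primary outcome is compromised. The endpoints concerned are exploratory. Severity is minor to moderate.

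**What to change.** Add a paragraph to the SAP, as exploratory analysis. The document is written in the past tense, so label the additions post hoc if the data had already been seen.

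1. Regress synthesis (mg/day) separately on:
   - mean 24-hr urinary oxalate from the two fixed-diet collections before the infusion, in mg/day;
   - the same in mg/g creatinine;
   - fasting hourly urinary oxalate, defined as the single pre-infusion hourly urine. If infusion-period urines are also used, count ¹²C-oxalate only.

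   The infusion-day 24-hr aggregate is left out because it contains infused tracer and spans a fasted period.
2. Keep the planned creatinine and lean mass models. State which collection supplies creatinine, and whether lean mass comes from impedance or DEXA, since the protocol describes both.
3. For every model report slope, intercept, residual SD and 95% prediction interval. Leave-one-out error is optional.
4. Report all candidates, and do not present the best-performing one as validated.
5. Base surrogate conclusions on prediction error, not on r or p<0.05.
6. Optionally, give the mean difference between synthesis and 24-hr oxalate in mg/day as a description, with the caveat about dietary oxalate. Limits of agreement are not required.

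The cost is a paragraph of text and a few lines of SAS; the measurements are already collected. The downsides are that surrogate precision will look less favourable than a correlation p-value, that residual SDs will be imprecise at this sample size, and that additions made after the data were seen carry less weight.
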